FDA	Food and Drug Administration
Gb3	Globotriaosylceramide
GDPR	General Data Protection Regulation
GI	Gastrointestinal
GVP	Good Pharmacovigilance Practice
HCP	Healthcare Professional
HRQoL	Health-related quality of life
HTA	Health Technology Assessment
IEC	Independent ethics committee

IQR	Interquartile range
IRB	Institutional review board
ISPE	International Society for Pharmacoepidemiology
IV	Intravenous
LOE	Lack of Effect
LVMi	left ventricular mass index
MI	Myocardial infarction
MRI	Magnetic Resonance Imaging
PC	Product Complaint
PQC	Product quality complaint
SAP	Statistical analysis plan
SD	Standard deviation
SF-12	12 Item Short Form Survey
SF-36	36 Item Short Form Survey
SS	Special Situations
STROBE	Strengthening the reporting of observational studies in epidemiology
TIA	Transient ischaemic attack
WBC	White Blood Cell
WHO-5	World Health Organization-5 Wellbeing Index
WPAI	Work Productivity and Activity Index
WPAI-CG	Work Productivity and Activity Index: Caregiver

2. Key definitions

Episode of care: An episode of care is an element or part of the care or treatment pathway which is being studied or measured. For the purpose of this study, an episode of care will constitute all healthcare professional (HCP) activities involved in the preparation and administration of a single dose of enzyme replacement therapy (ERT) with agalsidase alfa and agalsidase beta, including ERT (and pre-medication) preparation, pre- and post-administration assessment, pharmacy and clinic activities, and any follow up activities.

Caregiver: in the context of this study a caregiver is defined as an individual aged 18 years or over who has a personal relationship with and provides informal (unpaid) care, support or assistance to someone diagnosed with Fabry Disease, and accompanies them to the hospital or treatment centre for ERT administration on one or more occasion during the study data collection period. For example, this may be a parent, spouse/ partner, son/ daughter, other relative, neighbour or friend.

3. Responsible parties

The names, titles, degrees, addresses and affiliations of all responsible parties, including the Principal Investigators, co-investigators, and a list of all participating centres, Study Management Company and Sponsor contacts will be maintained in a separate document.

4. Abstract

Title	A multi-country time and motion study to describe the experience of clinicians, patients and their caregivers during the treatment of Fabry Disease with Enzyme Replacement Therapy with agalsidase alfa and agalsidase beta
Rationale for study	
Enzyme replacement therapy (ERT) with agalsidase alfa (Replagal®, Shire or biosimilar) or agalsidase beta (Fabrazyme®, Sanofi Genzyme or biosimilar) is the current mainstay of treatment for patients with Fabry Disease (FD). Both ERT preparations need to be administered as an intravenous (IV) infusion every two weeks. Migalastat (Galafold®, Amicus Therapeutics), an orally-administered treatment for patients with FD with amenable mutations, is now approved in a number of countries.
 
As oral therapies for FD become available, there is a need for comprehensive information about the burden of current treatments from the perspective of both patients and their caregivers and healthcare providers, to enable them to make fully informed decisions about the most appropriate treatment strategy. There is currently a paucity of data on the true resource burden associated with use of existing ERT and the wider impact of attendance for ERT on health-related quality of life (HRQoL) and work productivity.
 
The present study will address these evidence gaps by generating robust real world data to quantify the current burden of ERT for the treatment of FD across four countries. The study will utilise a time and motion methodology to measure the total healthcare professional (HCP) time associated with a single episode of ERT administration, with patient- and caregiver-reported outcomes including HRQoL, wellbeing, levels of fatigue, work productivity and the strain of providing care, to be collected directly from patients with FD and their caregivers. The data may be utilised by Amicus Therapeutics in submissions to Health Technology Assessment (HTA) bodies, and will

	be useful for HCPs to inform future treatment decisions and ongoing patient management.
Research question and hypothesis	What is the total HCP time associated with the preparation and administration of a single dose of ERT in patients with FD and the patient and caregiver time and costs associated with an ERT attendance? What is the impact of FD on patients' HRQoL, wellbeing, levels of fatigue and work productivity? What is the burden of care provision for the caregivers of patients with FD and the impact on their work productivity? This is a descriptive study and there is no a priori hypothesis to be tested.
Objectives	
Primary objective
 
To quantify the total time spent by HCPs in the preparation and administration of a single dose of ERT (with agalsidase alfa and agalsidase beta) in patients with FD.
 
Secondary objectives
 
 1. To quantify the total patient time, costs (i.e. out of pocket expenses) and work-related absence associated with attendances for the administration of a single dose of ERT (with agalsidase alfa and agalsidase beta) in patients with FD. 2. To quantify the total caregiver time, costs (i.e. out of pocket expenses) and work-related absence associated with accompanying a patient with FD for the administration of a single dose of ERT (with agalsidase alfa or agalsidase beta). 3. To describe patient-reported HRQoL (measured by the 12 Item Short Form Survey [SF-12]), wellbeing (measured by the World Health Organization-5 Wellbeing Index [WHO-5]), levels of fatigue (measured by a bespoke Fatigue Likert scale) and work productivity (measured by the Work Productivity and Activity Index [WPAI] questionnaire) in patients with FD treated with ERT. 4. To describe work productivity (measured by the WPAI for caregivers [WPAI:CG]) and the strain of care provision (measured

	by the Caregiver Strain Index [CSI]) in caregivers of patients with FD treated with ERT.
Study design	
This is an international, non-interventional research study of adult patients with FD and their caregivers. The study will comprise a prospective time and motion evaluation and a cross-sectional evaluation of patient and caregiver-reported outcomes. Patients' demographic characteristics will be collected from hospital medical records.
 
For the cross-sectional evaluation of patient and caregiver-reported outcomes, patients with FD and their caregivers will be asked to complete a series of questionnaires, to include validated measures of HRQoL, wellbeing and work productivity (for patients) and work productivity and the strain of care provision (for caregivers). Patients and caregivers will also complete a bespoke questionnaire to evaluate the total time associated with attending the hospital or treatment centre for a single ERT administration visit, and time away from work. In addition, patients will also be asked about their level of fatigue using a bespoke Likert scale. With the exception of the work productivity questionnaire and Fatigue Likert scale, the study questionnaires will be completed at a single point in time, when the patient attends the hospital or treatment centre for administration of ERT. The work productivity questionnaire (which has a recall period of seven days, excluding the day of completion) will be completed twice; the first work productivity questionnaire will be completed 1-7 days after receiving a dose of ERT (ideally within 2 days), to capture a seven day period that includes an ERT administration visit and the second questionnaire will be completed on the day the patient attends the hospital or treatment centre to receive their next dose of ERT (to capture a seven day period that does not include ERT administration). The Fatigue Likert scale will be completed three times; during an ERT administration visit, on the evening of the visit and the next day.

	Separate patient consent will be obtained for the time and motion evaluation and for the cross-sectional evaluation of patient-reported HRQoL, wellbeing, levels of fatigue and work productivity; thus, patients who do not wish to complete the study questionnaires will remain eligible for the time and motion study (and vice versa), provided that consent has been obtained.
Setting	Patients with FD who are receiving ERT and their caregivers will be identified and recruited from approximately 12 specialist centres in four countries (Taiwan, Turkey, Brazil and Japan).
Participants	
The target sample size for the time and motion evaluation undertaken as part of this study is 240 ERT episodes, including 60 ERT episodes (30 for agalsidase alfa and 30 for agalsidase beta) in each participating country. Ideally, a maximum of two ERT administration episodes will be observed per patient; as such, at least 30 patients are expected to be enrolled in each country. For countries with limited FD patient numbers, a review of episodes of care observed will be completed on an ongoing basis. It may be determined that it is possible to observe three episodes per patient in these circumstances, however only two episodes will be observed per patient wherever possible.
 
For the questionnaire evaluation, approximately 120 patients and 20 caregivers will be expected to fill questionnaire sets (approximately 30 patients' and 5 caregivers' questionnaire sets per country).
 
Patient inclusion criteria
 
 • Patients aged 18 years old or over at time of consent. • Patients with a documented diagnosis of FD. • Patients who have received ≥ 4 doses of ERT (with agalsidase alfa or agalsidase beta) for the treatment of FD. • Patients who present to the participating hospital(s) or treatment centre(s) for administration of a dose of ERT (as part of their routine treatment) during the data collection period.

	
Patient exclusion criteria
 
 • Patients aged <18 years at time of consent • Patients who are unable or unwilling to give consent for study participation. • Patients whose ERT preparation and administration takes place exclusively in the home setting with no HCP involvement in preparation of the infusion. • For the time and motion evaluation: Patients whose ERT is administered by a HCP who does not consent to be observed. 
Caregiver inclusion criteria:
 
 • Aged 18 years of age or over at time of consent. • Self-identifies as a caregiver of a patient with FD for whom written informed consent has been obtained for inclusion in the study. 
Caregiver exclusion criteria
 
 • Caregiver (and/or the patient with FD whom they support or care for) is unable or unwilling to give consent for study participation. 
Staff inclusion criteria (for time and motion study):
 
 • Members of the whole care team responsible for administering agalsidase alfa and agalsidase beta to patients with FD. • Staff who have given written consent to be observed during the provision of care. 
Participant selection
 
Consecutive eligible patients (and their caregivers) presenting at the participating centres during the prospective recruitment period will be included in the study until the required sample size (number of ERT episodes) is reached. For patients who are eligible to be observed more than once (for the time and motion study), initial consent for observation of up to three episodes of care will be obtained, and will be confirmed verbally by their HCP before the second episode of care.

--	--

	Each patient and caregiver will only be asked to complete one set of questionnaires (with the exception of the work productivity questionnaire [which will be completed twice] and the fatigue Likert questionnaire [which will be completed three times], as described above).
Data source(s)	
Patients' demographic and clinical data will be sourced from patients' medical records and other systems within the main (specialist) participating FD centres and extracted into electronic case report forms (eCRFs).
 
For the time and motion component of the study, prospective data relating to HCP time associated with the preparation and administration of a single dose of ERT will be captured by direct observation of HCPs by an independent external researcher or a member of the patients' care team, during the episode of care and recorded on a paper case report form (CRF) which will then be transcribed into an eCRF.
 
Patient- and caregiver-reported outcomes will be reported directly by patients and caregivers using anonymised-coded paper-based questionnaires which will be transcribed into an Excel database by central data managers.

Study time period(s)	
It is anticipated that the prospective recruitment / data collection period for this study will be approximately 4-5 months, starting from the date on which the relevant approvals to conduct the study are in place. A maximum of three episodes of care per patient during the data collection period will be included. Consenting patients with FD and their caregivers will be asked to complete the study questionnaires at the time points described above.

Study endpoints	Primary endpoint: Summary measures of the total time spent by HCPs in the preparation and administration of a single dose of ERT in patients

	
with FD; stratified by country and by ERT product (agalsidase alfa or agalsidase beta).
 
Main secondary endpoints:
 
 ● Summary measures of the time spent by HCPs on each separate task associated with the preparation and administration of a single dose of ERT (with agalsidase alfa or agalsidase beta). ● Summary measures of the total patient time and costs associated with attendance for the administration of a single dose of ERT (with agalsidase alfa or agalsidase beta). ● Proportion of patients with work absence due to attendance for this ERT episode and number of hours absent. ● Summary measures of the total caregiver time and costs associated with accompanying a patient with FD for the administration of a single dose of ERT (with agalsidase alfa or agalsidase beta). ● Proportion of caregivers with work absence due to accompanying the patient for this ERT episode and number of hours absent. ● Summary measures of patients': 
 ○ HRQoL (SF-12 scores / responses). ○ General wellbeing (WHO-5 scores / responses). ○ Level of fatigue (Fatigue Likert scale) ○ Levels of work impairment (WPAI scores / responses). ● Summary measures of caregivers': 
 ○ Levels of work impairment (WPAI-CG scores / responses). ○ Level of strain in providing care for a patient with FD (CSI scores / responses).
--	---

5. Study amendments and updates

All amendments to the protocol will be documented in Table 1.

Protocol deviations will be documented in a Protocol Deviation Log (maintained in a separate document).

Table 1. Study amendments

Amendment number	Date of amendment	Section amended	Amendment description	Reason for amendment
1	Click here to enter a date.		None at present	
2	Click here to enter a date.			
3	Click here to enter a date.			
4	Click here to enter a date.			

6. Milestones

Table 2. Study milestones

Milestone	Planned date(s)/frequency
Planned regulatory approval activities	Start: Jun 2019 End: Aug 2020
Planned start of study (date of first consent)	Jun 2020
Planned collection of first data point	Jun 2020
Planned collection of last data point	Nov 2020
Study progress report 1	No progress report is planned
Interim study report 1	No interim analysis is planned
Registration in EU Post-authorisation study Register or equivalent public database	Clinical trials.gov; Feb 2020
Final report of study results (end of study)	Apr 2021

7. Rationale and background

Fabry disease (FD) is a rare inherited lysosomal disorder caused by deficiency or dysfunction of the enzyme α -galactosidase A, which leads to an accumulation of globotriaosylceramide (Gb3) within the lysosomes of many cell types leading to cellular dysfunction and multi-organ disease¹. FD is associated with a number of characteristic clinical signs and symptoms including neuropathic pain, gastrointestinal complications, headaches, impaired sweating, vertigo, hearing impairment, angiokeratomas and cornea verticillata². Over time, FD can lead to irreversible organ damage and is a cause of premature renal failure, heart disease, cerebrovascular events and death³. As X-linked disorder, male sufferers of FD tend to be more severely affected than females⁴. Patients with FD are widely reported to have reduced health related quality of life (HRQoL) compared with the general population^{5,6} due to the debilitating symptoms and damage to vital organs. Increasing age, classical FD phenotype, more severe disease and pain have been identified as major contributors to reduced HRQoL⁶.

Enzyme replacement therapies (ERT) with agalsidase alfa (Replagal®, Shire) and with agalsidase beta (Fabrazyme®, Sanofi Genzyme) currently represent two treatment options for patients with FD and have been shown to reduce substrate levels in several cell types. In addition there are reports of reductions in the severity of neuropathic pain, stabilization of renal and cardiac function and delay in the occurrence of serious complications^{7–10}. However, both ERT preparations need to be administered as an intravenous (IV) infusion every two weeks and therefore lifelong ERT places a considerable burden on patients, their caregivers and healthcare services. ERT administered in the hospital or clinic setting requires frequent visits for IV infusions, which many patients find stressful and inconvenient; furthermore, hospital-based treatment often takes place in a specialist FD centre, which may be a considerable distance from the patient's home^{11,12}. In some countries ERT can be administered in the patient's home under certain circumstances (for example, if the patient has stable disease and experienced no adverse reactions during hospital-based infusion) and this is generally perceived to be more convenient than hospital-based therapy^{11–13}, can improve treatment compliance¹⁴ and may help to reduce the burden on healthcare services. However, even home-based ERT administration can cause disruption to a patient's daily activities and usually requires a healthcare professional (HCP) to supervise the infusion. To mitigate risk of adverse effects associated with ERT, patients are also frequently administered pre-medications with antihistamines and low-dose corticosteroids, which can be an added burden to patients.

Therapeutic options for FD have expanded over the past few years, with the development of orally-administered medicines such as Migalastat (Galafold®, Amicus Therapeutics) which has received regulatory approval in several countries. In this context, there is a need for comprehensive information about the burden of standard-of-care ERT treatments from the perspective of both patients and their caregivers and healthcare providers, to enable them to make fully informed decisions about the most appropriate treatment strategy. There is currently a paucity of data on the true resource burden associated with use of existing ERT and the wider impact of attendance for ERT on HRQoL and work productivity. Although data are available about the overall frequency and cost of ERT attendances^{15,16}, there have been no published data on the total time and cost involved for patients, caregivers and HCPs. In

addition, the impact of receiving ERT on work productivity has been described in market research¹⁷ and qualitative research¹⁸ but has not been formally quantified.

The present study will address these evidence gaps by generating robust real world data to quantify the current burden of ERT for the treatment of FD across four countries. The study will utilize a time and motion methodology to measure the total HCP time associated with an episode of ERT administration, with patient- and caregiver-reported outcomes including HRQoL, wellbeing, work productivity and caregiver strain, to be collected directly from patients with FD and their caregivers. The data may be utilized by Amicus Therapeutics in submissions to Health Technology Assessment (HTA) bodies, and will be useful for HCPs to inform future treatment decisions and ongoing patient management.

8. Research questions and objectives

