
 ● Summary measures of the total patient time associated with attendance for the administration of a single dose of ERT (with agalsidase alfa or agalsidase beta) in patients with FD. To include: ● Time spent travelling to and from the hospital or treatment centre ● Time spent collecting ERT from pharmacy (where relevant) ● Time from arrival in hospital/treatment centre to departure ● Time from arrival in hospital/treatment centre to start of ERT infusion ● In addition, if the patient started/delivered their ERT infusion at home following set-up at a primary healthcare centre, the 	
Patient responses to the bespoke study questionnaire:
 
 ● Patient ID ● Date of episode ● Patient employment status (employed full time / employed part time / unemployed / retired / student / home-maker) ● Were they accompanied to the hospital or treatment centre (by a relative or caregiver) or did they attend alone (accompanied / alone) ● Time left home/work to travel to hospital or treatment centre ● Time arrived at hospital or treatment centre ● Time of start of ERT infusion.

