
following will also be included in the total patient time:
 
 Duration of ERT infusion and any home-based post-administration activities. Time spent travelling to and from treatment centre after ERT infusion (only if patient returned to treatment centre after ERT infusion) Time spent at treatment centre after ERT infusion. Summary measures of the total cost to patients (i.e. out-of-pocket expenses) associated with attendance for the administration of a single dose of ERT (to include the costs of travel / parking / subsistence / other costs). Distribution of patient employment status and whether the patient attended the ERT administration visit accompanied by a relative/caregiver or alone. Proportion of patients with work absence due to attendance for this ERT episode and number of paid / unpaid hours absent. 	
 Time left hospital or treatment centre to travel back to home/work. Time arrived back at home/work. 
Whether patient returned to work on the day of the infusion or the following day. If the patient started their ERT infusion at home following set-up at a primary healthcare centre, the following will also be collected:
 
 Start and end time of ERT infusion Start and end time of any post-administration activities. Time left home/work to return to hospital or treatment centre (if relevant) Time arrived back at hospital or treatment centre (if relevant) Time left hospital or treatment centre to travel back to home/work Time arrived back at home/work Did patient take any time off work to attend this ERT episode? If yes, number of paid / unpaid hours absent from work. Number of hours worked during ERT infusion (if relevant). Costs (i.e. out-of-pocket expenses) incurred by the patient that were directly related to this ERT administration episode (to include
--	--

	costs of travel / parking / subsistence / any other costs).
Secondary objective 2: To quantify the total caregiver time costs (i.e. out-of-pocket expenses) and work-related absence associated with accompanying a patient with FD for the administration of a single dose of ERT (with agalsidase alfa or agalsidase beta).	

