
 Summary measures of the total caregiver time associated with accompanying a patient with FD for the administration of a single dose of ERT (with agalsidase alfa or agalsidase beta). To include: Time spent travelling to and from the hospital or treatment centre Time spent collecting ERT from pharmacy (where relevant) Time from arrival in hospital/treatment centre to departure Time from arrival in hospital/treatment centre to start of patient's ERT infusion In addition, if the patient started/delivered their ERT infusion at home following set-up at a primary healthcare centre, the following will also be included in the total caregiver time (if the caregiver was involved in the activity): Duration of ERT infusion and any home-based post-administration activities. Time spent travelling to and from treatment centre after ERT infusion (only if patient returned to treatment centre after ERT infusion and was accompanied by a caregiver) 	
Caregiver responses to the bespoke study questionnaire:
 
 • Caregiver ID and patient ID • Date of episode • Caregiver sex (male / female) • Caregiver age category (<20 years / 20<30 years, 30<40 years, 40<50 years, 50<60 years, 60<70 years, 70<80 years, 80 years or over) • Does the caregiver also have FD? • Caregiver employment status (employed full time / employed part time / unemployed / self-employed / retired / student / home-maker) • Caregiver relationship to patient (parent / spouse or partner / son or daughter / other relative / friend or neighbour) • Type and frequency of care or support provided by the caregiver to the patient with FD • Time left home/work to travel to hospital or treatment centre • Time arrived at hospital or treatment centre • Time of start of ERT infusion

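### Total patient and caregiver time counts the whole visit, and neither Table 4 nor the SAP separates time spent on other care during the same visit

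*Protocol*

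**What the plan says.** The protocol (Abstract, Study design) has patients and caregivers complete a "bespoke questionnaire to evaluate the total time associated with attending the hospital or treatment centre for a single ERT administration visit".

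Protocol Table 4 (section 9.6) defines the patient endpoint as "Summary measures of the total patient time associated with attendance for the administration of a single dose of ERT" and lists its components. These are travel both ways, pharmacy collection where relevant, and "Time from arrival in hospital/treatment centre to departure". The clock points run from "Time left home/work to travel to hospital or treatment centre", through "Time left hospital or treatment centre to travel back to home/work", to arrival back at home or work. The caregiver endpoint, "Summary measures of the total caregiver time associated with accompanying a patient with FD for the administration of a single dose of ERT", has the same structure. When the infusion is set up at a primary healthcare centre and run at home, the total is a sum of segments, but the time at the centre is still counted whole.

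SAP 2.6 (Secondary Objectives 1 and 2) takes differences between these time points and summarises them. It has no term for other care.

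Two neighbouring measures are limited to ERT. Patient costs are those "incurred by the patient that were directly related to this ERT administration episode", with a parallel limit for caregiver costs. HCP time covers only activities relating to preparing and giving ERT (section 9.1.1).

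**The concern.** A patient who has an infusion and a cardiology scan on the same day contributes the scan, any wait for it and the whole journey to total patient time. So does the caregiver who stays. Nothing in the listed dataset marks such a visit, and no eligibility criterion removes it.

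Combined visits are plausible. The protocol's background says "hospital-based treatment often takes place in a specialist FD centre, which may be a considerable distance" from home, the disease affects several organs, and the study leaves routine management unchanged.

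Both totals are main secondary endpoints, and the protocol says the data may be used in HTA submissions. Extra minutes of this kind can only raise the apparent burden of ERT, and a larger sample does not reduce them. Section 9.10 rules out queries on patient- and caregiver-reported data, so a gap in the form cannot be filled later.

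**Working it through.** **1. Attribution rule by measure**

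| Measure | Limited to ERT? | Where |
|---|---|---|
| HCP time | Yes | Protocol 9.1.1; Table 4, primary objective |
| Patient and caregiver costs | Yes | Table 4, secondary objectives 1 and 2 |
| Patient and caregiver time | No: whole interval plus travel | Table 4, secondary objectives 1 and 2; SAP 2.6 |

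**2. Size of the excess**

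Excess in the mean = share of visits with other care × mean minutes of that care not overlapping ERT activity.

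The documents give neither input, so both are assumed. For the low end, infusions every two weeks (protocol section 7) give 52/2 = 26 visits a year. One or two combined reviews a year would then be 1/26 = 3.8% to 2/26 = 7.7% of visits, so I start at 5%. The upper end of 30% and the range of 30-120 minutes are assumptions.

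| Share of visits | 30 min | 60 min | 120 min |
|---|---|---|---|
| 5% | 1.5 | 3 | 6 |
| 10% | 3 | 6 | 12 |
| 20% | 6 | 12 | 24 |
| 30% | 9 | 18 | 36 |

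The range is 1.5 to 36 minutes, with 12 minutes at 20% and 60 minutes.

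**3. A loose yardstick**

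The documents give no expected value or precision for total patient or caregiver time. Table 5 covers only pre-administration, infusion and post-administration time. Its figures can be reproduced with SD = range/4 and half-width = t(0.975, n−1) × SD/√n × √(1 − n/N), where N = 5015 for Brazil.

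- About 30 patient questionnaire sets are expected per country (section 9.8), so n = 30/2 = 15 per product if evenly split.
- Alfa: range 10+15+40 = 65 to 30+30+60 = 120 min, SD = 55/4 = 13.75. The half-width is 7.60 min. Table 5 prints 84m54 to 100m06, half-width 7m36, which agrees.
- Beta: range 10+15+90 = 115 to 30+30+180 = 240 min, SD = 125/4 = 31.25. The half-width is 17.28 min. Table 5 prints 160m13 to 194m47, half-width 17m17, which agrees.

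An excess of 12 minutes is 12/7.60 = 1.6 times the alfa half-width and 12/17.28 = 0.7 times the beta half-width. The full range, 1.5 to 36 minutes, is 0.2 to 4.7 times for alfa and 0.1 to 2.1 times for beta.

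This shows only that the excess could be negligible or could exceed sampling error. Total patient time also contains travel, which adds its own spread. With about 5 caregivers per country, no such comparison is useful for them.

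**The case against.** The strongest reply is that the plan measures what it says it measures. Objective 1 concerns time associated with attendances, objective 2 concerns accompanying the patient, and arrival to departure is a listed component. This stands: door-to-door time is a valid attendance measure and should be kept. A reader might infer that the endpoint is wrongly defined, and the objectives do not support that. What remains is that attendance time and time attributable to ERT differ when visits are combined, and the plan offers no way to tell them apart.

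Second, the forms cannot be checked. Only the Annex 2 heading is in the available text, and Table 4 calls its response categories provisional. This also stands. Even if the forms ask the question, SAP 2.6 does not use the answer.

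Third, a reader might infer that combined visits are common. The documents do not say so. Section 7 says only that treatment is often at a specialist centre that may be distant, section 9.2 allows community centres, and Table 4 asks for the closest earlier laboratory and cardiac values without saying they were taken on infusion days.

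Fourth, some apparent extra time belongs to the episode. Pre- and post-administration assessment and follow-up are in its definition (protocol section 2), and other care given while the patient waits for ERT or is being infused adds no minutes. The calculation therefore counts non-overlapping minutes only.

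Fifth, there is partial protection. Travel is a separate component. The observer also records patient arrival in, and departure from, the clinic for ERT administration. No rule links those times to total patient time, and patients who consent only to questionnaires have none.

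**Conclusion.** The point holds as a gap in attribution. As listed and derived, total patient and caregiver time cannot be divided into ERT and other care, and any non-overlapping other care raises it. The direction is certain if visits are combined. The size is not known: 1.5 to 36 minutes on the mean rests entirely on the assumed 5-30% of visits and 30-120 minutes.

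Two stronger conclusions are not supported:

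- A reader might divide the excess by the Table 5 means and get up to 36/92.5 = 38.9% for alfa or 36/177.5 = 20.3% for beta. Those means exclude travel, so such percentages overstate the relative error in total patient time.
- A reader might infer a false country or product difference. Local habits of combining visits could contribute to one, but the plan makes no comparisons between subgroups or treatments (section 9.9.2), and section 9.11 already acknowledges country differences in settings and care processes. Section 9.11 does not mention this upward bias.

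The primary endpoint, HCP time, is not affected. This is a worthwhile correction to descriptive secondary endpoints.

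**What to change.** - **Forms.** Unless the Annex 2 questionnaires already ask it, add one item to each bespoke form: whether any other appointment, test or treatment took place on this visit and, if so, its start and end time.
- **SAP 2.6, Secondary Objectives 1 and 2.** Keep door-to-door attendance time as the stated measure. Report beside it the time excluding other-care minutes that do not overlap waiting for ERT, the infusion, or its pre- and post-administration assessment. Flag travel time for visits where ERT was not the only reason to attend.
- **If the forms are already in use.** For patients in both study parts, match the questionnaire to the observed episode by patient ID and date, and compare the on-site interval with the observed clinic arrival and departure times. The difference is a ceiling on other care outside the clinic, since it may also contain waiting and a consultation held elsewhere. Add the upward bias to section 9.11.

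The cost is one question on forms designed for this study and one derivation rule. The downsides are a slightly longer form and some recall error in the added item.
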